### 10.1. Exposure to Study Treatment

The duration of exposure (days) will be summarized using descriptive statistics by treatment group for DB phase, DBext phase and combined.

- Duration of exposure to IP (days) = (last treatment date – first treatment date + 1) – total duration of temporary IP discontinuation

The duration of each incidence of temporary IP discontinuation will be calculated as follows:

- Duration of temporary discontinuation of IP = Date of restart of IP - Date of temporary discontinuation of IP + 1.

The total duration of temporary IP discontinuation is the sum duration of temporary discontinuation of IP over each incidence of discontinuation.

Total subject exposure to IP (mg) will be calculated by adding the doses taken by a subject during the DB phase, DBext phase, and combined and will be summarized using descriptive statistics. Duration of exposure to IP (days) will be categorized to following intervals: 1-21, 22-42, 43-84, 85-126, 127-168, 169-210, 211-252, 253-294, 295-336, 337-420, 421-504, 505-588, 589-672, 673-756, and >756 days. Number and percent of subjects in each interval will be tabulated by treatment group.

At each IP administration, the subject will be asked to record the reason for dose adjustment (if any). If the subject has multiple dose adjustments caused by the same reason, the subject is only counted once per reason category. Reasons for dose adjustment will be summarized by treatment group for the DB phase, DBext phase, and combined.

## 10.2. Treatment Compliance

Subject's overall compliance (%) with IP will be calculated as follows:

- (number of tablets consumed during study / number of tablets expected to be consumed during study) \*100

where

- number of tablets expected to be consumed during study = total number of weeks on 5 mg once weekly + 2\*total number of weeks on 5 mg or 10 mg twice weekly; during the period from first treatment date to last, inclusive

and

- number of tablets consumed during study = sum of drug taken weekly by a subject during the DB phase, DBext phase, and combined

Treatment compliance with IP will be summarized by treatment group using descriptive statistics for DB phase, DBext phase, and combined. Number and percent of patients with compliance of <60%, 60% to <80%, 80% to 120%, and >120% will be tabulated by treatment group for DB phase, DBext phase, and combined.

Subject treatment compliance will be listed based on drug administration data.

## 10.3. Adverse Events

Per ICH E6 (R2), an adverse event (AE) is any untoward medical occurrence in a patient or clinical investigation subject administered a pharmaceutical product and which does not necessarily have a causal relationship with this treatment. An AE can therefore be any unfavorable and unintended sign (including an abnormal laboratory finding), symptom, or disease temporally associated with the use of a medicinal (investigational) product, whether or not related to the medicinal (investigational) product.

AEs will be mapped to preferred terms (PTs) and system organ classes (SOCs) using MedDRA dictionary version 24.0. Subjects experiencing the same event more than once will be counted only once at the most severe grade and the closest relationship to study treatment.

AEs related to COVID-19 will be flagged.

### 10.3.1. Treatment-emergent Adverse Events

An AE is defined as a treatment emergent adverse event (TEAE) if it meets one or more of the following criteria:

- An AE starting on or after the first study drug dose and within 30 days after the last dose of study drug.

- An AE occurring prior to the first study drug dose that worsens (increase in grade) after the first study drug dose.

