## 10. SAFETY ANALYSES

Safety analyses include exposure to study treatment, treatment-emergent adverse events, clinical labs, electrocardiograms (ECGs), vital signs, and any abnormal findings observed during physical examinations after study enrollment and through discontinuation of study treatment +30 days. Safety analyses will be performed using the Safety population including by treatment groups, as defined in [Section 4.3](#) and pooled across all active dose levels. No inferential comparison of safety endpoints will be performed, unless otherwise specified.

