#### 10.3.4. TEAE Analyses

The counts and percentages of subjects experiencing a TEAE and TEAEs by PTs and SOCs in the following categories will be presented by study treatment arm:

All AE summaries will be restricted to TEAEs. Each AE summary will be displayed by treatment group for DB phase, DBext phase, and combined. Summaries that are displayed by SOC and PT will be ordered by descending order of incidence of SOC and PT within each system organ class.

Summary tables of the following TEAEs will be presented:

- Overall summary of TEAEs
- Patient incidence of TEAEs and the total number of entries by SOC and PT. This summary will be repeated for subgroups specified in [Section 10.10](#).
- Patient incidence of TEAEs by SOC, PT, and highest severity. At each level of patient summarization, a patient is classified according to the highest severity if the patient reported 1 or more events. AEs with missing severity will be considered severe for this summary.
- Patient incidence of TEAEs by SOC, PT, and closest relationship to IP (Related/Not Related). Related AEs are those with relationships reported as “Definite,” “Probable,” or “Possible,” and unrelated AEs are those with relationships reported as “Unlikely” or “Not Related”. At each level of patient summarization, a patient is classified according to the closest relationship if the patient reported 1 or more events. AEs with a missing relationship will be considered related for this summary.
- Patient incidence of serious TEAEs and the total number of entries by SOC and PT.
- Patient incidence of TEAEs leading to IP withdrawal or study discontinuation by SOC and PT. This is a subset of the AEs where Action Taken with Study Treatment is checked as “Drug Withdrawn” or where “Patient Discontinued from Study” is checked on the eCRF.
- Patient incidence of COVID-19 related TEAEs.

Patient incidence will be summarized as subject counts and percentages unless otherwise specified.

The number of AEs and events per 100 patient years will be summarized by SOC and PT.

- Individual patient years = (the last recorded study visit date – first dose date +1)/365.25  
where: the last recorded study visit date = end of study date recorded on end of study CRF page for that patient
- Total patient years on study = sum of all individual patient years within the Safety Population
- Events per 100 patient years =  $\frac{\text{Number of Event} \times 100}{\text{Total Patient Years on Study}}$

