### Baseline and Change from Baseline

The baseline value for statistical analyses of quantitative parameters is defined as the mean of all available evaluations prior to the first administration of IP, unless otherwise specified. Values collected at unscheduled visits prior to the start of the IP administration will be included in the calculation of baseline values. If there is only one evaluation prior to the first administration of IP then the available data from this evaluation will be used as the baseline value.

The baseline value for analyses of lipid parameters is defined as the last fasted evaluation prior to the first administration of IP.

The baseline value for analyses of qualitative parameters (eg, normal/abnormal) is defined as the last evaluation prior to the first administration of IP.

Baseline values defined above will not change regardless if a subject stops taking IP and begins taking commercially marketed OCA.

Change from baseline = (post-baseline value – baseline value).

Percent change from baseline =  $100 * (\text{post-baseline value} - \text{baseline value}) / \text{baseline value}$

For the purpose of tabulations, the unscheduled post-baseline values generally will be excluded from summary tables, but will be included in data listings. Unscheduled visits will be considered for analyses of shift from baseline to worst value (low-normal-high).

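### The second TEAE criterion (SAP Section 10.3.1) has no end date, so off-drug worsening of a pre-dose AE can count as treatment-emergent when a new AE on the same day does not

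*SAP*

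**What the plan says.** SAP Section 10.3.1 makes the two criteria alternatives: "An AE is defined as a treatment emergent adverse event (TEAE) if it meets one or more of the following criteria".

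- Criterion 1, for new events: "An AE starting on or after the first study drug dose and within 30 days after the last dose of study drug".
- Criterion 2, for events already present: "An AE occurring prior to the first study drug dose that worsens (increase in grade) after the first study drug dose".

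The flag decides what is tabulated, because Section 10.3.4 states: "All AE summaries will be restricted to TEAEs". Listings in the same section cover all AEs.

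Three places in the SAP bear on observation after IP has stopped:

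- Section 5 tabulates withdrawal from treatment separately from withdrawal from the study, and also tabulates study status after treatment.
- Section 10.3.4 ends each patient's time on study at a date defined as "the last recorded study visit date = end of study date recorded on end of study CRF page for that patient", not at a fixed interval after the last dose.
- Appendix A (Baseline and Change from Baseline) provides for a switch to the marketed drug: "Baseline values defined above will not change regardless if a subject stops taking IP and begins taking commercially marketed OCA".

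The only other 30-day phrase concerning safety is in the opening of Section 10, where the list of safety analyses ends with "any abnormal findings observed during physical examinations after study enrollment and through discontinuation of study treatment +30 days".

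**The concern.** The upper limit in criterion 1 keeps events that arise well after dosing out of the treatment-emergent tables. Criterion 2 lacks it, so whether a late off-drug event counts depends on whether the condition was already recorded as an AE before the first dose. That has nothing to do with exposure to IP.

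Safety and tolerability are part of the primary objective (Section 2.1.1), and the flag feeds the tables by system organ class and preferred term, severity, relationship and seriousness. Sections 10.3.5 and 10.3.6 also define new or worsened treatment-emergent pruritus and fatigue partly through worsening of a baseline condition, which is the kind of event criterion 2 can govern.

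The provision for commercial OCA makes the gap more awkward. If a subject leaves IP, starts commercial OCA and then has a pre-dose AE worsen, the wording makes that event a TEAE of the study treatment however late it occurs.

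**Working it through.** The plan gives no figure to reproduce, so the check applies the definition as a logical rule.

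**Rule as written.** An AE is a TEAE if

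- (A) first dose ≤ onset ≤ last dose + 30 days, or
- (B) onset < first dose, and the grade increases after the first dose.

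**Test case.** Assume for illustration that the last dose is on Day 336 (Week 48: 48 × 7 = 336) and that AE data are still collected on Day 426. The gap is 426 − 336 = 90 days, which exceeds 30.

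| Event on Day 426 | (A) | (B) | TEAE? |
|---|---|---|---|
| Pre-dose AE increases in grade | No: onset precedes first dose | Yes | Yes |
| New AE starts | No: 90 > 30 | No: onset is not before first dose | No |

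The same split occurs for any event more than 30 days after the last dose.

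**Inside the window.** On Day 350 the gap is 350 − 336 = 14 days. The new AE meets (A) and the worsened AE meets (B), so both are TEAEs. The asymmetry exists only beyond 30 days.

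**Rule with the limit added to (B).** On Day 426 neither event is a TEAE. On Day 350 both are. The two kinds of event are then treated alike.

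**Does another section close the window?** Nothing else in the SAP amends the TEAE definition. The phrase in Section 10 starts its window at study enrollment, not at the first dose, and reads most naturally with physical-examination findings. It could also be meant as a general limit on safety analyses, but the text does not settle which.

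**What cannot be computed.** The number of events affected needs the length of AE collection after the last dose, the number of subjects with an AE open before dosing, the frequency of late worsening, and the way worsening is recorded. The SAP gives none of these.

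**The case against.** The strongest case against the point is that it may have little or no effect in practice.

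- *Few events may qualify.* Criterion 2 concerns something recorded as an AE before dosing. Screening lasts 14 to 28 days (Section 3), and Section 8 treats diseases that occurred before the first dose as medical history. If worsening of a long-standing condition is entered as a new AE with its own start date, criterion 1 and its limit already apply. Section 10.3.3 lists worsening of ascites as an event in its own right. The SAP does not say how worsening is recorded, so this stands as a limit on size.
- *AE collection may stop soon after the last dose.* Section 5 and the end-of-study date show that a status and a date are recorded, not that AEs are collected months later. The collection period is left to the protocol, which was not available for this review. This also stands.
- *Patients are counted once per event (Section 10.3).* A late worsening changes a table row only if that patient was not already counted there. No formal hypothesis is tested (Section 2.2), and no inferential safety comparison is planned unless otherwise specified (Section 10).

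None of this supplies the missing end date. It bears on how much the omission matters.

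A reader might infer three stronger claims that the SAP does not support.

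- *That criterion 2 contradicts Section 10.* If the 30-day phrase there belongs to physical-examination findings, there is no conflict. If it is a general limit, it may already be the intended bound on both criteria. Neither reading is proven.
- *That TEAE incidence is inflated by some number of percentage points, more in the arm with more early stopping.* Every input to such a figure would have to be invented.
- *That the rates per 100 patient-years are distorted.* Their denominator already runs to the end of study, so late worsenings fall in time that is already counted.

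**Conclusion.** The point holds on the wording and is minor. Criterion 2 in Section 10.3.1 has no upper limit, the criteria are alternatives, and the flag controls every AE summary. A programmer following the text would therefore classify late off-drug worsening and late new onset differently.

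The practical effect rests on two conditions that the SAP does not state: that AEs are collected more than 30 days after the last dose, and that worsening is kept on the original AE record rather than entered as a new AE. If either fails, the asymmetry has no effect. If both hold, some events will be misclassified, in a number that the SAP does not allow to be estimated and that may be small. The most likely explanation is a phrase left out in drafting.

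**What to change.** Give criterion 2 the same upper limit as criterion 1. Suggested sense: *a pre-dose AE whose grade increases on or after the first dose of study drug and no later than 30 days after the last dose*. Keep later worsening in the all-AE listing of Section 10.3.4, where it remains visible by patient.

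The cost is one phrase in the SAP and one extra condition in the TEAE flag, which needs the date of the grade increase. The downside is that a few late off-drug worsenings would appear only in the listing and not in the tables. The SAP is to be finalized before database lock (Section 1), so the change should be made by then.

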### 10.3.2. Serious Adverse Events

A serious adverse event (SAE) is any of the following untoward medical occurrences at any dose:

- Death
- Is immediately life threatening
- Requires in-patient hospitalization or prolongation of existing hospitalization
- Results in persistent or significant disability or incapacity
- Results in a congenital abnormality or birth defect
- Is an important medical event that may jeopardize the patient or may require medical intervention to prevent one of the outcomes listed above.

Events **not** considered to be SAEs are hospitalizations for:

- Routine monitoring of the studied indication and not associated with any deterioration in condition or AE;
- Elective treatment for a pre-existing condition that did not worsen;
- Respite care or observation when there is no AE associated with the hospitalization.

### 10.3.3. Adverse Events of Special Interest

The following decompensation events are adverse events of special interest:

- Variceal bleeding or recurrent variceal bleeding documented by endoscopy OR patient presenting with anemia or melena (hemoglobin drop  $\geq 2$  g/dL) and found to have varices documented by endoscopy, irrespective of hospitalization or requirement of blood transfusion.
- Gastrointestinal bleeding as a result of gastric or duodenal varices verified by endoscopy
- Hepatic encephalopathy, Grade  $\geq 2$
- New onset ascites requiring treatment
- Worsening of ascites (requiring increase in drug therapy or requirement of surgical procedure such as paracentesis or shunt placement)
- Refractory ascites -unresponsive to medications, and patient is not a candidate for TIPS or shunt and requires large volume paracentesis
- Hyponatremia ( $\text{Na} \leq 125$  mEq/L) secondary to ascites
- Spontaneous bacterial peritonitis (confirmed by diagnostic paracentesis- by cell count/chemistry)

- Hepatorenal syndrome Type 1 and Type 2 and Acute Kidney Injury (AKI)
- Liver failure defined as worsening of liver synthetic function that is persistently worse relative to baseline and/or progressive over time:
  - Hepato-pulmonary syndrome
  - Porto-pulmonary syndrome
  - Liver Transplant
  - Increase in MELD scores by 3 points relative to baseline, persistent over time and unrelated to vitamin K deficiency related increase in INR
  - Any liver related event that requires hospitalization and treatment

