### 9.6. Clinical Outcome Events

The following clinical outcome events will be captured in the study:

- Time from first dose to death (all cause)
- Time from first dose to liver-related death
- Time from first dose to liver transplant
- Time from first dose to MELD score  $\geq 15$  (for patients with MELD  $\leq 12$  at baseline)
- Time from first dose to earliest hospitalization for new onset or recurrence of:
  - variceal bleed
  - hepatic encephalopathy (as defined by a West Haven score of  $\geq 2$ )
  - spontaneous bacterial peritonitis (confirmed by diagnostic paracentesis)
- Time from first dose to uncontrolled ascites (diuretic resistant ascites requiring therapeutic paracentesis at a frequency of at least twice in a month)
- Time to first occurrence of any above listed clinical events

The incidence and time to first occurrence of any above listed clinical events will be summarized by treatment group using the log rank test stratified by the randomization stratification factor. The minimum and maximum time to clinical event will be presented. KM estimates of the

distribution of the time-to-event will be tabulated and graphed by treatment group. The tabulation will include the KM methodology using 25th, 50th (median), and 75th percentiles with associated 2-sided 95% CIs, as well as percentage of censored observations. The number and percent of patients censored and with events will be presented. The hazard ratio and 2-sided 95% CI will be estimated based on a Cox regression model stratified by randomization strata. The proportionality of hazards will be assessed using Schoenfeld residuals.

In addition, the incidence and time to each of the above clinical events, and the incidence and time to occurrence of HCC will be summarized by treatment group using the same methods as defined above.

For the time to event analyses, subjects who do not experience an event will be censored at the time of their last contact. Subjects with no data after randomization will be considered to have an event on Day 1 (first day of IP dosing). All time-to-event endpoints include only adjudicated events.

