The following listings will be presented by treatment group and patient:

- All AEs
- Serious AEs
- Severe AEs
- Treatment-related AEs
- AEs leading to Study Drug Withdrawal or Study Discontinuation
- AEs leading to Death
- TEAEs related to COVID-19
- Major adverse cardiovascular events (excluding deaths)

The original date and time will be shown on all listings of AEs.

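### Hepatic decompensation is the only AESI category in the SAP, but no AESI table or listing is planned, so no output counts patients with an AESI as Section 10.3.3 defines it

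*SAP*

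**What the plan says.** Section 10.3.3 introduces its list with "The following decompensation events are adverse events of special interest". The list covers variceal and other variceal gastrointestinal bleeding, encephalopathy of Grade 2 or higher, three forms of ascites, hyponatremia at or below 125 mEq/L secondary to ascites, spontaneous bacterial peritonitis, hepatorenal syndrome with acute kidney injury, and liver failure. Liver failure has five sub-items, one of them a persistent 3-point rise in MELD. Variceal bleeding counts "irrespective of hospitalization or requirement of blood transfusion".

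Section 10.3.4 then fixes the outputs. Under "Summary tables of the following TEAEs will be presented" it names seven summaries, including "Patient incidence of TEAEs and the total number of entries by SOC and PT". Under "The following listings will be presented by treatment group and patient" it names eight listings. COVID-19 events have a table and a listing, and major adverse cardiovascular events have a listing. Pruritus (10.3.5) and fatigue (10.3.6) have their own definitions, event-day analyses and Kaplan-Meier analyses.

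Section 9.6 separately plans incidence and time-to-event analyses by treatment group for clinical outcome events, with the condition "All time-to-event endpoints include only adjudicated events".

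**The concern.** The plan defines one AESI category in detail and then does not use it. The term does not return after Section 10.3.3. A reader of the resulting report could not find how many patients in each arm had any AESI, or how many met each criterion.

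Safety and tolerability against placebo is part of the primary objective (2.1.1), in Child-Pugh B and C patients. Section 1 says that analyses added beyond the SAP will be identified as post hoc. If the plan stays as it is, the arm comparison of its own AESIs falls under that label, and the rules for grouping terms and confirming laboratory criteria could be chosen after treatment codes are known.

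**Working it through.** No formula applies; this is a coverage check of the AESI list against every planned output that could carry it.

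**1. The AESI list (10.3.3).** There are ten top-level items. The tenth, liver failure, splits into five, so there are 9 + 5 = 14 separate terms.

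**2. AESI-specific outputs.** Summary tables in 10.3.4: 0 of 7. Listings in 10.3.4: 0 of 8. Sections 10.3.5 and 10.3.6 deal with pruritus and fatigue only, and the safety subgroups in 10.10 do not mention AESIs.

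**3. Overlap with the clinical outcome events (9.6).**

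| Coverage in 9.6 | AESI terms | Number |
|---|---|---|
| Counted outright, if adjudicated | Liver transplant | 1 |
| Counted in a narrower or different form | Variceal bleeding, encephalopathy, bacterial peritonitis (each only through hospitalization); refractory ascites (as ascites needing paracentesis at least twice a month); MELD rise (as reaching 15 or more from 12 or less) | 5 |
| No count of their own | Gastric/duodenal variceal bleeding, new-onset ascites, worsening ascites, hyponatremia, hepatorenal syndrome/AKI, hepato-pulmonary syndrome, porto-pulmonary syndrome, any liver-related event needing hospitalization and treatment | 8 |

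1 + 5 + 8 = 14. Two of the eight are partly touched: gastric or duodenal variceal bleeding where it is a hospitalized variceal bleed, and liver-related hospitalization where the cause is one of the three named in 9.6.

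**4. Could other outputs rebuild the count?**

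- *SOC/PT and serious TEAE tables (10.3.4).* They count coded terms by arm. A preferred term does not show encephalopathy grade, whether ascites needed treatment, sodium at or below 125 mEq/L, or a persistent 3-point MELD rise. No row is any decompensation.
- *Child-Pugh components (9.2, Table 2).* Ascites and encephalopathy categories are counted at each scheduled visit. Encephalopathy Grades 1 and 2 share a category, so Grade 2 or higher cannot be separated. The ascites categories carry no treatment criterion.
- *MELD (9.1).* Change from baseline and shift tables are planned. The lowest class is below 10 and the highest is 15 or more, so a 3-point rise within either class does not appear as a shift. Nothing tests persistence.
- *Chemistry (10.4).* Shift tables use low, normal and high, including to worst value. They do not use the 125 mEq/L threshold.

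**5. Illustration only.** The event counts are assumed and do not come from the SAP. About 50 patients randomized 1:1 gives 50/2 = 25 per arm. Suppose 6 OCA patients each have one decompensation event, spread over 5 to 6 preferred terms. Each term then shows 1 or 2 patients: 1/25 = 4% or 2/25 = 8%. As one AESI category the figure is 6/25 = 24%. This shows what a pooled row adds. The SOC rows and the 9.6 composite would regroup some of these patients, so it does not measure what would be missed.

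**The case against.** A reader might infer that decompensation is never counted by arm, or that an excess on OCA would not show in any table. The document does not support either. Section 9.6 plans a pooled composite by treatment group with a stratified log-rank test, Kaplan-Meier estimates and a Cox model, and the same for each component. The TEAE and serious TEAE tables count reported events by arm at both SOC and preferred-term level. Child-Pugh, MELD, sodium and creatinine summaries by arm do not depend on a site reporting an adverse event, and Appendix A brings unscheduled visits into the worst-value shifts. An arm difference would have several places to appear. This part of the objection stands and limits the point.

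It can also be said that the output list may be incomplete. The first sentence of 10.3.4 promises counts "in the following categories will be presented by study treatment arm", and no such list follows directly; text may have been lost when the file was read. The overall TEAE summary has no stated rows, so an AESI row is not excluded. The protocol may also describe AESI reporting. These are fair cautions. Even so, an unstated row is not a commitment, and one overall row would give neither counts by category nor a listing.

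Finally, calling decompensation the trial's main safety risk would go beyond the SAP, which only makes it the sole AESI category.

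**Conclusion.** The point holds as a gap in the planned outputs. AESIs are defined, but no AESI summary or listing is planned. What is shown by arm is a narrower adjudicated subset, individual terms and SOC rows, and related Child-Pugh, MELD and laboratory summaries. None gives the number of patients with any AESI, or with each category, as 10.3.3 defines them.

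The size is 0 of 7 summaries and 0 of 8 listings, with 8 of 14 AESI terms lacking their own count in 9.6. No effect on an estimate can be calculated, because the SAP gives no expected AESI rates. The conclusion assumes that the output lists in 10.3.4 are complete as they stand. It does not put any other safety analysis in doubt, but it should be corrected before unblinding.

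**What to change.** Add to Section 10.3.4:

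- a table of patient incidence and number of treatment-emergent AESIs, overall (any decompensation) and by 10.3.3 category, by treatment group, for the double-blind phase, the extension and both combined;
- an AESI listing, placed with the existing listings.

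State before unblinding how AESIs are identified, for example by eCRF flag, adjudication or derivation. For the two laboratory-based criteria already in 10.3.3 (sodium at or below 125 mEq/L and the persistent 3-point MELD rise), screen central laboratory data in both arms, and confirm attribution to ascites, or the absence of a vitamin K cause, by blinded review. Prespecify what persistence over time means for the MELD criterion. Requiring two consecutive assessments is one possibility; the choice is the sponsor's.

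A Kaplan-Meier analysis of time to first AESI, and dose regimen at onset in the listing, would be useful but are optional.

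The cost is SAP wording, one or two more outputs drawn mostly from data already collected, and a small amount of blinded medical review.
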